- **Embryo-Fetal Toxicity:** Based on findings from animal reproduction studies and its mechanism of action, capecitabine may cause fetal harm when given to a pregnant woman. Limited available data are not sufficient to inform use of capecitabine in pregnant women. In animal reproduction studies, administration of capecitabine to pregnant animals during the period of organogenesis caused embryoletality and teratogenicity in mice and embryoletality in monkeys at 0.2 and 0.6 times the exposure (AUC) in patients receiving the recommended dose respectively. Apprise pregnant women of the potential risk to a fetus. Advise females of reproductive potential to use effective contraception during treatment and for 6 months following the last dose of capecitabine.
- **Mucocutaneous and Dermatologic Toxicity:** Severe mucocutaneous reactions, some with fatal outcome, such as Stevens-Johnson syndrome and Toxic Epidermal Necrolysis (TEN) can occur in patients treated with capecitabine. Hand-and-foot syndrome (palmar-plantar erythrodysesthesia or chemotherapy-induced acral erythema) is a cutaneous toxicity. Median time to onset was 79 days (range from 11 to 360 days) with a severity range of grades 1 to 3 for patients receiving capecitabine monotherapy in the metastatic setting.

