4.2 Exclusion Criteria

1. Prior therapy with an anti-PD-1, anti PD-L1, anti-PD-L2, anti-CD137 antibody, or anti-cytotoxic T-lymphocyte-associated antigen-4 (CTLA-4) agents.
2. Chemotherapy, targeted small molecule therapy, experimental agents, prior therapy with anti-tumor vaccines or other immune-stimulatory antitumor agents, or biological cancer therapy (including monoclonal antibodies) within 14 days prior to the start of study drug, or not recovered (\leq grade 1 or baseline) from adverse events due to a previously administered agent.

3. Known CNS metastases and/or carcinomatous meningitis. Patients with radiated or resected lesions are permitted, provided the lesions are fully treated and inactive, patients are asymptomatic, and no steroids for treatment of CNS lesion have been administered for at least 30 days prior to the start of study drug.
4. Documented history of clinically significant autoimmune disease (other than well-controlled hypothyroidism) or a syndrome that requires systemic steroids or immunosuppressive agents. Subjects with vitiligo, type I diabetes mellitus, psoriasis not requiring systemic treatment, or conditions not expected to recur in the absence of an external trigger are permitted to enroll.
5. Receiving systemic steroid therapy or any form of immunosuppressive therapy within 1 week prior to the start of study drug. Note: Patients are permitted to receive up to 12 mg dexamethasone prior to administration of oxaliplatin and low dose steroids for up to 48 hours after dosing to prevent nausea and vomiting.
6. Received a live vaccine within 4 weeks prior to the start of study drug.
7. Has known history of, or any evidence of active, non-infectious pneumonitis.
8. Known history of HIV seropositivity, hepatitis C virus, acute or chronic active hepatitis B infection, or other serious chronic infection requiring ongoing treatment. Patients receiving prophylactic antibiotics (e.g., for prevention of urinary tract infection or chronic obstructive pulmonary disease) are eligible.
9. Pregnant or breastfeeding.
10. Not willing to use an effective method of birth control (refer to Section 6.5.1 for acceptable methods of contraception).
11. Concurrent severe and/or uncontrolled medical conditions, which may compromise participation in the study, including impaired heart function or clinically significant heart disease.

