5.7 Subject Discontinuation

Subjects will receive study treatment until treatment discontinuation for one of the reasons listed below. However, subjects may discontinue study treatment or withdraw their consent to participate in the study at any time without prejudice. All reasons for discontinuation or withdrawal from trial will be recorded.

The maximum duration of treatment for pembrolizumab will be up to 35 cycles. The duration of treatment for XELOX will be until unacceptable drug-related toxicity or disease progression. If capecitabine is not tolerated, monotherapy with pembrolizumab may be continued. Patients who complete 35 cycles of therapy and have complete response or prolonged stable disease may also elect to end therapy with capecitabine after a discussion with their treating physician and with approval of the PI. Re-introduction of oxaliplatin is permitted provided that neuropathy has improved. Reasons for subject discontinuation by the Investigator may include, but are not limited to, the following:

- Death
- Confirmed radiographic disease progression (Note: With approval of the Lead PI, a subject may be granted an exception to continue on study treatment with confirmed radiographic progression if clinically stable or clinically improved.)
- Significant noncompliance by subject or Investigator
- Investigator or Lead PI determination that it is no longer safe and/or no longer in the subject's best interest to continue participation
- Withdrawal of consent
- Lost to follow-up
- Necessity for treatment with other anticancer treatment prohibited by protocol
- Sexually active subjects who refuse to use medically accepted methods of contraception during the course of the study and for 120 days following the last dose of study drug
- Women who become pregnant or are breast feeding
- Request by regulatory agencies for termination of treatment of an individual subject or all subjects under the protocol
- The following **Treatment-Related Discontinuation Criteria** attributed to pembrolizumab:
 - Any Grade 2 uveitis, eye pain, or blurred vision that does not respond to topical therapy and does not improve to Grade 1 OR requires systemic treatment.
 - Recurrent Grade 2 pneumonitis
 - Any Grade 3 non-skin adverse event lasting > 7 days, with the following exceptions for treatment-related laboratory abnormalities, uveitis, pneumonitis, bronchospasm, diarrhea, colitis, neurologic toxicity, hypersensitivity reactions, and infusion reactions:

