6.5.1 Acceptable Concomitant Medications

All treatments that the Investigator considers necessary for a subject's welfare may be administered at the discretion of the Investigator in keeping with the local standards of medical care. All concomitant medication received from the date of signed informed consent through 30 days after the last dose of study drug should be recorded on the CRF including all prescription, over-the-counter (OTC), herbal supplements, and IV medications.

Abstinence is acceptable if this is the usual lifestyle and preferred contraception for the subject. Otherwise, subjects must agree to use two birth control methods after informed consent is signed through 120 days after the last dose of study drug. The two methods can either be two barrier methods or a barrier method plus a hormonal method to prevent pregnancy. The following are considered adequate barrier methods of contraception: diaphragm with spermicide (cannot be used in conjunction with cervical cap/spermicide), cervical cap with spermicide (nulliparous women only), contraceptive sponge (nulliparous women only), and male condom or female condom (cannot be used together). Appropriate hormonal contraceptives will include oral contraceptive pill (estrogen/progestin pill or progestin-only pill), contraceptive skin patch, vaginal contraceptive ring, or subcutaneous contraceptive injection.

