7.1 Dose Modifications

Subjects experiencing one or more AEs due to the study drug(s) may require dose modification(s) as described in [Section 7.1.1](#) and [Section 7.1.2](#). At the discretion of the Investigator, dose modifications are permitted outside of the those provided in the protocol if the Investigator feels it is in the interest of the subject's safety (e.g., due to multiple toxicities, persistent toxicities, intercurrent illness, or short term compliance or monitoring issues, etc.).

Subjects may need to be followed at least weekly when any study drug is held for toxicity until the toxicity returns to Grade ≤ 1 or is determined to be chronic or irreversible.

Dosing interruptions are permitted in the case of medical / surgical events or logistical reasons not related to study therapy (e.g., elective surgery, unrelated medical events, patient vacation, and/or holidays). Subjects should be placed back on study therapy within 4 weeks of the scheduled interruption, unless otherwise discussed with the Lead PI. The reason for interruption should be documented in the patient's study record. Dosing may be interrupted if there is a need for local palliative radiation therapy, with the approval of the lead PI. In this case, protocol-based therapy cannot be resumed until patients are at least 14 days out from the end of radiation.

If pembrolizumab is permanently discontinued, the subject will be discontinued from study treatment. Maximum duration of treatment for pembrolizumab will be up to 35 cycles. If patients discontinue oxaliplatin due to intolerance, they can be maintained on capecitabine and pembrolizumab. If capecitabine is not tolerated, pembrolizumab monotherapy may be continued. Re-introduction of oxaliplatin is permitted provided neuropathy has improved.

All dose modifications and reasons for modification must be recorded in the CRF.

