10.4.1 Pregnancy and Lactation

Although pregnancy and lactation are not considered adverse events, it is the responsibility of Investigator or designee to report any pregnancy or lactation in a subject (spontaneously reported to them), including the pregnancy of a male subject's female partner that occurs during the trial or within 120 days of following cessation of treatment. All subjects and female partners of male subjects who become pregnant must be followed to the completion/termination of the pregnancy. Pregnancy outcomes of spontaneous abortion, missed abortion, benign hydatidiform mole, blighted ovum, fetal death, intrauterine death, miscarriage and stillbirth must be reported as serious events (important medical events). If the pregnancy continues to term, the outcome (health of infant) must also be reported.

Such events must be reported reported in the same procedure as an SAE. Refer to SAE reporting procedures in [Section 10.2](#).

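### For women who could become pregnant, the required 120 days of contraception can end 61 to 64 days before the six months after capecitabine advised in the protocol's own safety text

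*Combined protocol and SAP*

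**What the plan says.** Two different periods appear in the protocol.

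- **Safety background.** Section 1.2.3 lists capecitabine's warnings from the package insert. Under embryo-fetal toxicity it states: "Advise females of reproductive potential to use effective contraception during treatment and for 6 months following the last dose of capecitabine".
- **Operative rule.** Section 6.5.1 accepts abstinence where that is the subject's usual lifestyle. Otherwise "subjects must agree to use two birth control methods after informed consent is signed through 120 days after the last dose of study drug".
- **Eligibility.** Exclusion criterion 10 in Section 4.2 sets no period of its own and points to that rule: "Not willing to use an effective method of birth control (refer to Section 6.5.1 for acceptable methods of contraception".
- **Discontinuation.** Section 5.7 lists refusal of contraception as a reason for discontinuation, with the period given as "during the course of the study and for 120 days following the last dose of study drug".
- **Pregnancy reporting.** Section 10.4.1 covers a pregnancy "that occurs during the trial or within 120 days of following cessation of treatment".

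The treatment rules determine which drug is taken last. Pembrolizumab is capped at 35 cycles, whereas for the chemotherapy Section 5.7 says "The duration of treatment for XELOX will be until unacceptable drug-related toxicity or disease progression". Section 7.1 adds that "If pembrolizumab is permanently discontinued, the subject will be discontinued from study treatment", but also that "If capecitabine is not tolerated, pembrolizumab monotherapy may be continued".

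**The concern.** The protocol reports that capecitabine may harm a fetus, with effects in mice and monkeys at 0.2 and 0.6 times patient exposure. It repeats the advice to continue contraception for six months, but the rule that participants agree to stops at 120 days. The documents give no reason for the shorter period.

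A woman who complies fully could therefore stop contraception while the safety text still advises it. Nothing scheduled later would catch this. The last planned pregnancy test is at the off-treatment visit 30 (±7) days after the last dose, and survival status afterwards may come from a phone call or a records review. The possible harm is to a fetus and would not be reversible. Section 1.2.3 gives the six-month period for women only, so the point does not extend to men.

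**Working it through.** No power or sample-size formula applies. The check is calendar arithmetic.

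**Inputs**
- Advised period after the last capecitabine dose: 6 months (Section 1.2.3).
- Required period after the last study drug: 120 days (Sections 6.5.1 and 5.7).
- Capecitabine is one of the study drugs (Section 6.4, under the Section 6.0 heading), so the 120 days can run from a capecitabine dose.
- In a standard cycle both infusions are on Day 1 and capecitabine runs through the evening of Day 14 (Sections 6.2.2, 6.3.2 and 6.4.2). Cycles last 21 days.

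**Six months in days.** Adding six calendar months to every date from 2017 to 2024 gives 181, 182, 183 or 184 days. For example, 1 January to 1 July in a non-leap year is 181 days, and 1 March to 1 September is 184.

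**Formula.** Let M be six months in days, and L the number of days from the last capecitabine dose to the last dose of any study drug.

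Shortfall = max(0, M − 120 − L)

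**Capecitabine taken last (L = 0).** 181 − 120 = 61 and 184 − 120 = 64, so 61 to 64 days. An ordinary final cycle is enough to produce this, because capecitabine continues for two weeks after the infusions. It also arises if the chemotherapy continues beyond the 35-cycle pembrolizumab limit.

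**Pembrolizumab continued alone.** Assume that the last capecitabine dose is on Day 14 of a nominal 21-day cycle. The next Day 1 is then 8 days later, and the k-th pembrolizumab-only dose falls at L = 8 + 21(k − 1).

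| Pembrolizumab-only doses (k) | L (days) | Shortfall (days) |
|---|---|---|
| 0 | 0 | 61–64 |
| 1 | 8 | 53–56 |
| 2 | 29 | 32–35 |
| 3 | 50 | 11–14 |
| 4 | 71 | 0 |

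**Sensitivity**
- Reading six months as 6 × 30 = 180 days gives a maximum of 180 − 120 = 60 days.
- If capecitabine stops early for intolerance, say on Day 5, the next Day 1 is 22 − 5 = 17 days later. One pembrolizumab-only dose then leaves 61 − 17 = 44 to 64 − 17 = 47 days.
- The ±3-day visit window shifts these values slightly.
- From L = 64 there is no shortfall on any start date.

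**The case against.** The strongest reply is that the six months is label text in a background section, addressed to the prescriber, and not a trial requirement. On this view 120 days is a trial minimum and both periods can be observed, since nothing tells a woman to stop at 120 days. Section 1.2.3 also refers readers to the current package insert, capecitabine comes from commercial supply, and the consent form, which is not available here, may state the longer period. It is right that the six months is not itself a trial rule. But a general pointer to prescribing information does not displace an explicit 120-day rule. Where the protocol wants the insert followed for a specific action, it says so in the operative text, as Section 6.4.2 does for dosing in renal impairment. Section 6.5.1 has no such link.

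Four narrower points have some force:
- Section 5.7 counts 120 days in addition to the course of the study, and survival follow-up might be read as part of that course. Section 10.4.1 has the same ambiguity. Both are therefore weaker support, and the point rests on Section 6.5.1.
- Section 6.5.1 asks for two methods where the label text asks only for effective contraception. That is stricter in kind but does not make up for a shorter duration.
- The stepped figures depend on the Day 14 assumption. The maximum does not.
- The number of women affected may be very small. Enrolment is open from age 18, however, and pregnancy testing is scheduled for women of childbearing potential, so the protocol expects some.

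**Conclusion.** The concern holds. The binding contraception period is shorter than the one in the protocol's own capecitabine safety text, by at most 61 to 64 days per affected woman. The shortfall is at its maximum when capecitabine is the last study drug, and falls to zero if pembrolizumab alone continues long enough.

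The size assumes that six months means calendar months and that the term study drug in Section 6.5.1 includes capecitabine. The number of women affected cannot be derived from the documents. This is a participant-safety and consistency matter that should be corrected; it does not affect the endpoints, sample size or analysis.

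**What to change.** Amend Sections 6.5.1 and 5.7 so that females of reproductive potential use contraception through the later of (a) 120 days after the last dose of any study drug and (b) six months after the last capecitabine dose. Leave the 120 days as it stands for other subjects. State the same end point for these women in the Section 10.4.1 reporting window, so that the contraception and reporting periods agree. Exclusion criterion 10 needs no change, because it refers to Section 6.5.1.

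This brings the shortfall to zero whichever drug ends last. The cost is protocol wording, consent wording if the consent form repeats 120 days, and up to about two more months of contraception for the women concerned. No visits or analyses are added.

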1.3 Study Rationale

This is a single arm, phase II study to assess the safety, tolerability, and efficacy of the RPTD of the combination of pembrolizumab, oxaliplatin and capecitabine in patients with previously untreated metastatic esophagogastric adenocarcinoma. The study will be conducted in two stages: 1) safety validation and 2) dose expansion. In the dose expansion cohort, the first cycle will be modified to allow one week of pembrolizumab monotherapy before starting XELOX chemotherapy, which will allow analysis of biomarkers related to pembrolizumab.

Gastric cancer is likely a PD-1 sensitive tumor type. The KEYNOTE-012 study was a Phase 1b study evaluating the use of pembrolizumab in gastric cancer patients. This study, conducted in the United States, Israel, Japan, South Korea, and Taiwan, screened 162 patients to identify 65 (40%) that were PD-L1 positive. Thirty-nine of these patients (19 from Asia Pacific and 20 from rest of the world) were enrolled and treated with pembrolizumab 10mg/kg every 2 weeks. The therapy was generally well tolerated with the most common adverse events being hypothyroidism and fatigue; few Grade ≥ 3 events were noted. There were 8 (22%, 95% CI 10-39) centrally confirmed partial responses, 13 (33%, 95% CI 19-50) investigator assessed partial responses, and 17 patients (53%) with at least one post-baseline tumor assessment that showed disease response. The median duration of response 40 weeks,

median overall survival was 11.4 months (95% CI 5.7 – not reached), and proportion of patients alive at 6 months was 42% (95% CI 25 – 59)¹⁶. Pembrolizumab is now in phase III studies as monotherapy in 2nd/3rd line gastric cancer.

The fluoropyrimidine/platinum combination is a common first line therapy for metastatic gastric cancer and it is considered “preferred” by the NCCN Gastric Cancer Guideline committee¹⁷. This combination can either be fluorouracil plus oxaliplatin or capecitabine plus oxaliplatin¹⁸⁻²⁰. Given the toxicity associated with cisplatin and the non-inferiority data from REAL2²¹, many clinicians prefer to use the less toxic and more convenient capecitabine/oxaliplatin combination. There are several studies evaluating the capecitabine/oxaliplatin doublet in the treatment of metastatic gastric cancer as well as others that have evaluated the doublet as a backbone for the addition of newer agents – as in this study²²⁻²⁶. In addition, it has recently been appreciated that many chemotherapeutic agents augment anti-tumor responses. Oxaliplatin in particular has been reported by many labs to induce so-called ‘immunogenic cell death’²⁷⁻²⁸. Thus, the combination of pembrolizumab and oxaliplatin can be considered a novel strategy for targeting the immune system for the treatment of advanced gastric cancer. In addition, the effects of pembrolizumab in advanced gastric cancer have not yet been well defined. The overall goals of this study are to both determine the activity of pembrolizumab + XELOX and to explore the immunological mechanisms of sensitivity and resistance to this therapy in patients with advanced gastric cancer with Duke collaborators who have experience in the analysis of immune markers, both in tumor tissue and in peripheral blood.

2.0 OBJECTIVES

2.1 Primary Objective

The primary objective of this trial is:

1. To describe the progression free survival (PFS) associated with the combination of pembrolizumab, oxaliplatin and capecitabine (pembro+XELOX) in all patients with previously untreated metastatic esophagogastric adenocarcinoma.

2.2 Secondary Objectives

The secondary objectives of this trial are:

1. To describe the safety and tolerability of the combination of pembro+XELOX in patients with previously untreated metastatic esophagogastric adenocarcinoma.
2. To describe the response rate (RR) and overall survival (OS) of the combination of pembro+XELOX in patients with previously untreated metastatic esophagogastric adenocarcinoma.

2.3 Exploratory Objectives

The exploratory objectives of this trial are:

1. To explore changes in CD8 and PDL1 expression in tumor tissue related to pembrolizumab treatment.
2. To explore other changes in tissue and blood based biomarkers and their correlation with clinical outcomes.
3. To explore changes in immune cells and biomarkers in those who completed treatment and remain in complete response.

3.0 STUDY DESIGN

3.1 Study Description

This is a single arm, phase II study to assess the safety, tolerability, and efficacy of the recommended phase II dose (RPTD) of the combination of pembrolizumab, oxaliplatin and capecitabine in patients with previously untreated metastatic esophagogastric adenocarcinoma. The study will be conducted in two stages: 1) safety validation and 2) dose expansion. Approximately 50 subjects may be accrued to ensure the trial obtains 5 evaluable subjects in the safety validation cohort and 30 evaluable subjects in the dose expansion cohort. Patients will be enrolled at the Duke Cancer Institute and select external collaborating institutions (dose expansion cohort only).

- Enrolled subjects are defined as subjects who give informed consent.
- Screen failures are defined as subjects who give informed consent and do not meet eligibility criteria.
- Accrued subjects are defined as subjects who give informed consent and meet eligibility criteria.
 - Withdrawal: Subject accrued but later withdrawn from the study, either before or after receiving a study drug.
 - Evaluable: In the Safety Validation Cohort, subjects who are accrued, received study treatment, and completed the first cycle of safety assessments or have dose limiting toxicity (DLT) which is study treatment related that precludes completing the full cycle of assessments will be considered evaluable for DLT. All subjects (in Safety Validation and Dose Expansion) who are accrued and receive any study treatment will be considered evaluable for toxicity. All subjects in Safety Validation and Dose Expansion who are accrued and receive any study treatment will be considered evaluable for efficacy.
 - Non-evaluable: In the Safety Validation Cohort, subjects who accrued but did not complete the first cycle of safety assessments due to reasons other than study treatment-related toxicity (e.g. disease progression or inter-current illness) are considered non-evaluable for DLT.

Table 3.1 Cohorts

Cohort	No. Evaluable Subjects	Oxaliplatin mg/m ² IV, Day 1 every 21 days*	Capecitabine mg/m ² PO, BID Days 1-14 every 21 days*	Pembrolizumab mg IV, Day 1 every 21 days*
Safety Validation	5	130	850 or 1000**	200
Dose Expansion	30	130	850 or 1000**	200

*For dose expansion cohort, Cycle 1, biomarker cycle, is 28 days in length. Cycles 2 and beyond are 21 days.

**The dose of capecitabine is per treating physician discretion. 850mg/m² and 1000mg/m² are preferred doses for the regimen in US patients based upon safety. While safety and activity in gastric cancer for capecitabine, particularly with oxaliplatin, in US vs non-US patients have not been systematically reviewed, most US doctors and many phase III protocols allow flexibility in dosing of capecitabine for this reason²⁹⁻³¹.

